## **7.4 Reporting Procedures**

### **7.4.1 SAE Reporting**

- Clinical coordinators will notify the principal investigator immediately when a SAE is discovered, in addition to filling out a standardized SAE form that will be reviewed and signed by the principal investigator (see section 7.3.3 above regarding SAE documentation).
- The principal investigator will then report any deaths to the institutional review board at the University of California San Francisco, the independent Data and Safety Monitor (DSM), and the NCCIH program officer within 24 hours of awareness of the event.
- Other unexpected serious adverse events that are potentially intervention-related will be reported by the principal investigator to the UCSF IRB, the DSM, and the NCCIH Program Officer within 48 hours of learning of the event.
- Anticipated or unrelated SAEs will be handled in a less urgent manner but will also be reported to the UCSF IRB and the DSM within 1 week of awareness of the event, and at least quarterly to the NCCIH Program Officer. Of note, no SAEs that are directly related to the study procedures are currently anticipated.

#### **7.4.2 Non-Serious AE Reporting**

- If a clinical coordinator discovers an AE that does not meet the definition of a SAE but may still pose a substantial risk of harm to a participant and is potentially associated with study interventions or procedures, he/she will report the AE to the principal investigator within 1 working day, in addition to filling out a standardized AE form.
- Cumulative trends in all non-serious adverse events will be reviewed by the principal investigator and the DSM at scheduled DSM meetings (see below for DSM meeting schedule). More frequent review of non-serious adverse events may be performed if recommended by the DSM or desired by the principal investigator.
- Although the UCSF IRB does not require reporting of non-serious AEs to the UCSF IRB, the principal investigator may consult the UCSF IRB for input on handling of non-serious AEs if they may still pose a substantial risk of harm to a participant or are potentially associated with study interventions or procedures.

#### **7.5 Follow-up for AEs/SAEs**

From the time that they are first reported by participants until the end of the study, AEs and SAEs will be followed until resolved or considered stable. At each scheduled follow-up contact after initial discovery of an AE or SAE, a clinical coordinator will assess whether the AE or SAE is continuing or has resolved, and will update information about event status on the AE or SAE form, as appropriate. For SAEs, the clinical coordinator or principal investigator will also make more active attempts to communicate with participants in between scheduled study visits (with their permission) in order to monitor resolution of SAEs.

#### **7.6 Independent Safety Monitoring**

The conduct of the study and safety of participants will be evaluated by an independent Data and Safety Monitor (DSM), [name], MD, MPH, Senior Research Scientist at Kaiser Permanente Northern California, who is a clinical researcher experienced with designing, implementing, and monitoring safety in therapeutic interventions studies as well as a practicing clinician. The DSM is independent of the investigators and staff participating in the study, and has no financial ties to the outcome of the study. The DSM will periodically review the conduct and outcomes of the study and provide feedback to the investigators, with particular attention to protecting the safety of the participants.

Prior to initiation of the trial, the DSM will review and approve the study design and plans for recruitment, adherence, interventions, data quality, and safety monitoring. At periodic intervals during the course of the trial, the DSM will evaluate the adequacy and timeliness of participant recruitment, adherence to the protocol, and the potential of the study to meet the stated goals; evaluate the quality and integrity of the data, including adequacy of data management and data security procedures; evaluate participant safety including trends in adverse events and relationship to the study procedures; consider factors external to the study when relevant information, such as scientific developments, may have an impact on the safety of the participants or the ethical conduct of the study; and make recommendations, if

necessary, to the investigators, the UCSF IRB, and the NCCIH on continuation, termination, or other modifications of the study protocol.

The DSM will periodically review aggregate and unblinded trial data according to the Data and Safety Monitoring Plan (DSMP). An emergency meeting may also be called by the principal investigator at any time should questions of participant safety arise. Each review will include an assessment of the adequacy and timeliness of participant recruitment, adherence to the visit and intervention protocols, data quality and timeliness, adverse effects, and participant safety. Interim reports for the DSM will be prepared by an unblinded biostatistician at the Women's Health Clinical Research Center, and sent to the DSM at least 5 days prior to a pre-scheduled meeting or conference call.

After each interim review, the DSM will provide a signed statement that indicates whether the study should continue, terminate, or be altered based on ability to meet study recruitment and data quality goals and participant safety. He will include any recommendations for changes to the protocol if necessary to enhance participant safety or potentiate the ability of the trial to answer the research hypotheses. This statement will be provided to the principal investigator and will be sent to the UCSF IRB and to the NCCIH program officer. All materials, discussions, and proceedings of the DSM process will be completely confidential.

## **8. INTERVENTION DISCONTINUATION**

Participation in the yoga therapy and/or physical conditioning interventions may be discontinued if determined to be necessary to protect the safety of a participant. The decision to discontinue the therapeutic intervention will be made on a case-by-case by the principal investigator, with input from the DSM if needed. Possible reasons for discontinuation of the therapeutic intervention may include: 1) development of a clinically significant adverse event limiting a participant's ability to safely take part in yoga or physical conditioning practice; 2) disruptive behavior exhibited by a participant during group yoga or physical conditioning classes or study visits that endangers the safety or comfort of other study participants, class instructors, or study staff; or 3) decision to terminate the study by the IRB, NCCIH, or other regulatory bodies.

In the event that the yoga therapy or physical conditioning control intervention is discontinued, participants will continue to be followed through the 24-week mail-in assessment (or early termination visit) to collect outcomes data, provided that the participant is willing and the principal investigator (with input from the DSM, if appropriate) judges that it is safe and feasible to do so. If follow-up assessments are continued, no modifications to the schedule of follow-up assessments will be made unless necessary to protect the safety of participants or to accommodate limitations in function resulting from an adverse event. Follow-up assessments in participants who have discontinued the therapeutic interventions will not include continue evaluation of adherence to group classes or home practice, assessment of yoga posture or practice adherence self-efficacy, or independent evaluation of participants' success in performing yoga postures.

## **9. STATISTICAL CONSIDERATIONS**

### **9.1 General Design Issues**

A parallel-group, superiority trial design has been selected as the being the most appropriate for the overall scientific goals of this research. Although this pilot trial will

not be powered to prove or disprove any scientific hypotheses, it will provide a means of testing and refining procedures for a future full-scale parallel-group superiority trial to determine the efficacy of the therapeutic yoga intervention for improving urinary incontinence in middle-aged and older women.

To control for the time and attention that participants will spend on group classes and home practice, a physical conditioning exercise program has been selected as an active behavioral control intervention for this trial. Although this control program may offer non-specific benefits for participants' overall health, the investigators believe that it is unlikely to substantially improve women's incontinence. Inclusion of the physical conditioning program will also minimize differential expectations of treatment benefit between the two groups, in an effort to promote equal adherence to study interventions and visits in both groups.

## **9.2 Sample Size and Randomization**

The investigative team plans to randomize and monitor up to 90 participants, with approximately 45 randomized to the yoga therapy group and 45 to the physical conditioning control group. No formal sample size estimates or power analyses have been performed for this pilot study, as one of the goals of this pilot is to collect preliminary data that may be used to guide sample size estimates for a larger clinical trial, if indicated. Study data on the standard deviation, intra-class correlation, and between-group difference in change in incontinence frequency and other efficacy outcomes will be used to guide sample size projections for a future full-scale trial powered to detect a 25% greater reduction in incontinence frequency associated with yoga therapy.

## **9.3 Intervention Assignment Procedures**

Randomization to the yoga therapy or physical conditioning control group will be performed by computer algorithm, with proof of eligibility required before assignment. Randomization will be implemented using randomly permuted blocks of sizes 2 and 4, and will also be stratified by clinical type of incontinence (i.e., stress, urgency, or mixed), to ensure adequacy of randomization within types. To avoid manipulation, standard allocation concealment procedures will be followed. A study analyst will prepare sealed, opaque envelopes containing group assignment, numbered consecutively with the randomization sequence numbers. At the baseline visit, when eligibility and incontinence type have been confirmed, coordinators will enter the date, participant name, and study ID in the randomization log and select the next numbered envelope to determine group assignment. All envelopes will be retained for review; randomization dates and times should follow the order of the sequence numbers, providing a check on validity. Although participants cannot be blinded to treatment assignment (due to the behavioral nature of the intervention), diary and questionnaire data used to evaluate the primary and secondary efficacy outcomes will be abstracted by blinded analysts.

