#### **4.3 Study Enrollment Procedures**

Recruitment: Participants will be recruited from the greater San Francisco Bay area using a multi-component approach that has been employed successfully in past clinical trials led by the investigators. This includes community-based media efforts (newspaper and radio advertisements, notices posted in community and senior centers, mass community mailings), recruitment from a database of women who have given permission to be contacted for women’s health research studies based at the University of California San Francisco, and posting of recruitment fliers in clinician offices (such as general internal medicine, geriatrics, gynecology, or alternative medicine).

Recruitment will be organized in waves to assemble successive cohorts of women who are confirmed to meet all eligibility criteria and who are available to attend upcoming group yoga or physical conditioning classes. Based on past experience, the investigators assume that three waves will be needed to recruit and randomize at 60 eligible participants, with up to three months of recruitment required per wave, and 15 to 20 eligible women randomized in each wave. This will allow for a minimum of ~8 women taking part in each class series in each intervention group.

Screening: Preliminary eligibility will be determined by research coordinators through a Screening Telephone Interview followed by an in-person Screening Clinic Visit. During the Screening Telephone Interview, coordinators will follow a standardized screening interview script to assess preliminary eligibility related to age, gender, incontinence history, and exclusionary conditions and medications and document reasons for ineligibility on the screening interview form (see section 6.2.3, Screening Procedures, for more detail). Candidates who appear preliminarily eligible at the end of the screening telephone interview will be scheduled to attend an in-person Screening Clinic Visit. After providing written informed consent at this visit, women will undergo more detailed assessment of incontinence symptoms, use of clinical incontinence therapies, exclusionary medical conditions, exclusionary medications, urine dipstick and pregnancy testing (for women of childbearing potential), and brief physical function assessment (see description of study procedures below), with reasons for eligibility or ineligibility documented on the screening clinic intake form.

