At the end of the Screening Clinic Visit, women who appear eligible will be given a blank voiding diary and instructions for completing it at home over a 3-day period and returning it to study staff at a Baseline Clinic Visit. Those who are confirmed to have stress-predominant, urgency-predominant, or mixed urgency-stress incontinence occurring at least 3 times over the 3-day diary period and meet all other inclusion/exclusion criteria at the Baseline Clinic Visit will be considered eligible for randomization to one of the two intervention groups.

**Randomization:** During each recruitment/randomization wave, eligible women will be randomized in a 1:1 ratio to one of the two intervention groups. Randomization will be stratified by clinical type of incontinence (i.e., stress, urgency, or mixed), to ensure adequacy of randomization within these three types. Randomization will be implemented by computer algorithm using randomly permuted blocks of sizes 2 and 4, with proof of eligibility required before assignment. To avoid manipulation, standard allocation concealment procedures will be followed (see section 6.2.4. on Randomization for more detail).

To avoid excessive lag time between randomization and the start of the yoga therapy or physical conditioning programs, randomization will take place within two weeks of the yoga or physical conditioning program orientation session. For candidates whose Baseline Clinic Visit falls within this two-week window, randomization will take place directly at the Baseline Clinic Visit. For candidates who complete their Baseline Clinic Visit more than two weeks before the start of the yoga or physical conditioning intervention programs, a Randomization Telephone Call will be scheduled to complete randomization within the two-week window.

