#### Baseline Clinic Visit

- Candidates will return with the completed 3-day voiding diary, and results will be reviewed by a clinical coordinator. Candidates whose diaries indicate predominantly urgency, stress, or mixed-type incontinence, document at least 3 incontinence episodes per 3-day diary, and meet all other eligibility criteria will be eligible to continue.
- Women will complete structured questionnaires about anxiety and perceived stress, incontinence-specific quality of life, and sleep quality.
- Physical function will be assessed by direct physical mobility evaluation.
- Participants will be given a brief written pamphlet about usual first-line behavioral management of incontinence (see description in interventions section above).
- If the Baseline Clinic Visit takes place within 2 weeks of the start of the yoga or physical conditioning program orientation session, eligible participants will be randomized to one of the two interventions at this visit.
- If the Baseline Clinic Visit takes place more than 2 weeks before the start of the yoga or physical conditioning program, eligible participants will be scheduled for a Randomization Telephone Call within two weeks of the start of the program to determine their intervention assignment.

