#### **6.2.4 Randomization and Blinding**

##### Randomization

Women who are confirmed to be eligible and available to take part in upcoming yoga or physical conditioning group class series will be randomized in a 1:1 ratio to one of the two intervention groups. Randomization will ideally take place within 1 month of completion of screening procedures, and in no cases will be able to take place more than 2 months after completion of screening procedures. Randomization must also take place within 2 weeks of the start of yoga or physical conditioning class series. If the Baseline Clinic Visit occurs within 2 weeks of the start of the yoga therapy or physical conditioning program, eligible participants will be randomized to one of the two interventions directly at this visit. If the Baseline Clinic Visit occurs more than 2 weeks before the start of the intervention program, eligible participants will be scheduled for a Randomization Telephone Call within two weeks of the start of the program to determine their intervention assignment.

During the Baseline Clinic visit or during the Randomization Telephone Call

(whichever is appropriate), randomization will be performed according to a pre-established computer-algorithm using randomly permuted blocks of sizes 2 and 4 (limited block size to ensure that the number of randomized participants within each strata always exceeds the block size).

Randomization will be stratified by clinical type of incontinence (i.e., stress, urgency, or mixed) to ensure adequacy of randomization among women with each major incontinence type. Randomization will be implemented. Prior to randomization, the research coordinator will complete a randomization checklist confirming that the participant meets all eligibility criteria.

Additionally, participants' availability and willingness to attend upcoming yoga or physical conditioning group classes will be re-confirmed before randomization assignment is obtained.

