Standard allocation concealment procedures will be followed to avoid manipulation of randomization. Prior to the start of recruitment, the randomization scheme will be developed by a statistical programmer who will have no contact with participants or role in data entry, cleaning, or analysis. To execute the randomization scheme, a research assistant who will also have no contact with participants or access to study data will then prepare a series of sealed, opaque envelopes containing group assignment, numbered consecutively with the randomization sequence numbers. When the participant is ready for randomization, study coordinators will enter the date, participant name, and study ID in the randomization log and select the next numbered envelope corresponding to the participants' type of incontinence (stress-, urgency-, or mixed-type) to determine group assignment. Once a participant has been randomized, she cannot be re-assigned to a different intervention group. All randomization envelopes will be retained for review; randomization dates and times should follow the order of the sequence numbers, providing a check on validity.

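### Do Sections 6.2.4 and 9.3 leave it unclear who prepares the randomization envelopes and when they are opened?

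*Combined protocol and SAP*

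**What the plan says.** Two sections describe how a woman receives her assignment.

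- **Who prepares the envelopes.** In Section 6.2.4 a statistical programmer writes the scheme, and then "a research assistant who will also have no contact with participants or access to study data will then prepare a series" of sealed envelopes. Section 9.3 has: "A study analyst will prepare sealed, opaque envelopes containing group assignment, numbered consecutively with the randomization sequence numbers". It places no limit on that analyst's contact with participants or data.
- **When the envelope is opened.** Section 9.3: "At the baseline visit, when eligibility and incontinence type have been confirmed, coordinators will enter the date" and take the next envelope. Section 6.2.4 sets a time limit: "Randomization must also take place within 2 weeks of the start of yoga or physical conditioning class series". If the baseline visit is earlier than that, Section 6.2.3 (Baseline Clinic Visit) says "eligible participants will be scheduled for a Randomization Telephone Call within two weeks of the start of the program to determine their intervention assignment". Section 4.3 and the footnote to the table in 6.2.7 also provide for the call.

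The sections agree on blocks of 2 and 4, stratification by incontinence type, sealed and consecutively numbered opaque envelopes, a randomization log and retention of the envelopes. Section 9.3 closes by stating that "diary and questionnaire data used to evaluate the primary and secondary efficacy outcomes will be abstracted by blinded analysts".

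**The concern.** Participants know their group and the primary outcome is a diary that they fill in themselves. Protection against bias therefore rests largely on concealed allocation and blinded abstraction.

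Elsewhere in the protocol, analysts are the staff who abstract post-randomization diaries and enter outcome questionnaires (Sections 6.1.1 and 10.1). If one of them filled the envelopes, that person could know the arm behind each sequence number and later abstract diaries. Section 6.2.4 rules this out by keeping the preparer away from study data. Section 9.3, read alone, does not.

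The timing difference touches Aim 1. The two-week rule has a stated purpose: "To avoid excessive lag time between randomization and the start of the yoga therapy or physical conditioning programs". A wave may take some time to fill, "with up to three months of recruitment required per wave", so many baseline visits could fall before the window opens. Assigning those women at the visit would lengthen the wait between assignment and first class. Women lost while waiting might then count as drop-outs, against a limit of under 20% during the 12-week intervention.

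**Working it through.** The plan states no figure on this point, so the check is mainly a comparison of passages. The arithmetic then sizes the timing issue.

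**1. Preparer**

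- The two sections name different roles, so this is a true inconsistency.
- For harm to follow, the preparer must also abstract outcome data. Section 6.2.4 (Blinding) requires analysts who abstract efficacy outcomes to be blinded to allocation, and the last sentence of 9.3 repeats this. Using an envelope-filling analyst who knew the assignments as an abstractor would breach both.
- The preparer knows arms by sequence number, not by woman. The link is the randomization log, which coordinators complete. No section gives analysts access to that log.
- Abstracted forms are verified against the paper source by someone who did not enter the data (Section 10.3.2).

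**2. Timing**

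- Section 9.3 names the baseline visit. It does not say that assignment happens only there.
- Sections 4.3, 6.2.3 and 6.2.4 and the footnote in 6.2.7 all provide for the visit or the call. Section 6.2.4 makes the two-week limit mandatory.

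**3. Size, if 9.3 were followed alone on timing**

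Assume baseline visits spread evenly over the W weeks before classes start, and a constant weekly loss r among waiting women. Neither assumption comes from the documents.

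- Share of visits more than two weeks early: (W − 2)/W.
- Mean wait of those women: (W + 2)/2 weeks.
- Added loss: mean of 1 − (1 − r)^t for t uniform on 0 to W, minus the same mean with t capped at 2.

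Reading three months as W = 13 gives 11/13 = 85% of visits early, a mean wait of 15/2 = 7.5 weeks, and 2.3, 4.4 or 8.4 added points of drop-out at r = 0.5%, 1% or 2%.

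That case goes beyond what the protocol allows. Section 6.2.4 wants randomization within one month of completing screening and bars it after two months. Screening ends with the Baseline Clinic Visit (Section 6.2.1). Taking a month as 4.35 weeks:

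- Two-month limit: the earliest usable visit is 2 × 4.35 + 2 = 10.7 weeks before classes. In the even 13-week case, (13 − 10.7)/13 = 18% of the modelled women could not be validly randomized under 6.2.4 without renewed screening.
- One-month target: 4.35 + 2 = 6.35 weeks.

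| W (weeks) | Early visits | Mean wait (weeks) | Added loss at r = 0.5% / 1% / 2% (points) |
|---|---|---|---|
| 13 | 85% | 7.5 | 2.3 / 4.4 / 8.4 |
| 10.7 | 81% | 6.35 | 1.7 / 3.4 / 6.5 |
| 6.35 | 69% | 4.2 | 0.7 / 1.4 / 2.8 |

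Recruitment also includes telephone screening, the screening visit and the home diary, so baseline visits fall late in a wave. This again favors the lower rows.

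**The case for a change.** The strongest case for a change is that a faithful summary leaves detail out, whereas 9.3 names a different person for the same task. Only 6.2.4 expressly separates the preparer from study data. On timing, a coordinator who worked from 9.3 alone would break a mandatory rule for every early baseline visit. The telephone call is also no side route: it has its own column in the 6.2.7 table, and the credibility and expectations measure is scheduled only there. The pilot exists partly to refine procedures for a larger trial, and a cross-reference would cost very little.

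The textual point stands. Section 9.3 is wrong or incomplete on the preparer, and it omits both the call and the separate envelope series for each incontinence type. The consequence does not stand. The prominence of the call in Sections 4.3, 6.2.3, 6.2.4 and 6.2.7 makes it unlikely that staff would miss it. The blinding of abstractors is required independently of who fills envelopes. No section says that one person does both jobs. The drop-out figures need a coordinator to ignore all of those sections, loss rates that the documents do not supply, and a rule that losses before the first class count toward a limit headed as applying during the 12-week intervention. The protocol does not state such a rule.

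**Conclusion.** This is a clerical inconsistency in a condensed restatement, with no gain from treating it as a fault in the plan. Section 4.3 identifies 6.2.4 as the detailed procedure, and every other passage on timing agrees with it. A team that follows the whole protocol has concealed allocation, blinded abstraction and randomization within two weeks of the start. The expected effect on any estimate, feasibility rate or conclusion is nil.

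The figures above apply only if 9.3 is followed in isolation, and only under the assumed even accrual and 0.5% to 2% weekly loss. Within the one-month target they come to about 0.7 to 2.8 points of drop-out. The conclusion on the preparer assumes that the blinding rule in 6.2.4 is kept. A record that the envelope preparer had also abstracted outcome data while knowing the assignments would be a departure from the protocol, and would not show that the plan permits it.
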